12.9. Biomarker Assessment

Additional blood samples will be collected and stored for future biomarker analysis on Day 1, on Day 120 (\pm 30 days), on Day 240 (\pm 30 days), and on Day 330 (\pm 30 days). These samples are to be obtained prior to dosing and prior to breakfast.

Protocol-specific instructions will be provided to each site in a Study Lab Manual for the collection, handling, storage, and shipping of samples. The date and actual time each sample is collected will be recorded. Date and time of last dose prior to sample collection will also be recorded.

12.10. Other

12.10.1. Food Journal Requirement

While on study drug, subjects are recommended to avoid eating foods high in PUFAs. Subjects will keep food journals from screening through the completion of month 1 on study drug. After month 1, subjects will keep 2-week food journals prior to next scheduled onsite visit. Subjects (or parents/caregivers, as applicable) will have an initial call and as needed with the diet coach to discuss food journal completion requirements.

13. STUDY PROCEDURES AND SCHEDULE

All study visits, assessments, and procedures involving study subjects will be performed at a Sponsor-approved investigator site, and assessments and procedures will be performed by study personnel with the supervision of an Investigator. All measurements and results obtained as part of the protocol will be recorded in the CRF. The Schedule of Events is summarized in Table 1. It is recommended, but not required that the procedures should be completed in the order that they are listed to avoid causing fatigue to the subject. Each site visit can be done over multiple days as needed to accommodate for scheduling flexibility. Actual start times of all protocol assessments will be recorded.

13.1. Visit 1: Screening (Up to 30 Days)

Screening procedures can be performed from 30 to 14 days prior to the first dose on Day 1. A signed and dated ICF (or assent form) will be obtained from the subject as required by the protocol before any screening procedures are conducted. A signed copy of the ICF will be given to the subject. Screening procedures include the following:

- Evaluate eligibility per inclusion/exclusion criteria
- Perform a serum pregnancy test for all female subjects, unless there is documented evidence confirming they are not of childbearing potential
- Obtain blood samples for hematology, chemistry, coagulation, and lipid profile in a fasting state
- Obtain a urinalysis sample (dipstick test and microscopic examination if clinically indicated)
- Perform the exercise bike test (CPET should occur in the morning after fasting for a minimum of 2 hours {if the subject has had a meal/snack}, with neither caffeine nor nicotine for at least 12 hours before testing)
- Perform a FARS-Neuro and clinician-rated CGI (severity of illness question only)
- Record medical history and demographics
- Record the C-SSRS
- Complete the Speech Measurement Recording
- Perform a physical examination
- Record vital sign measurements, height, weight, and BMI
- Subject complete FARS ADL, SF-36, VAS (for Fatigue), Fatigue scale, Neuro-QoL scales, Speech Assessment Questionnaire and Fall questionnaire

- Obtain T1MW and T25FW
- Obtain an echocardiogram (LVEF) (To be performed if there has been no echocardiogram performed in the last 12 months before screening).
- Obtain a 12-lead ECG
- Sites to train subject on completion requirements for the Fall Diary
- Phone call with the diet coach to review food journal completion requirement

13.2. Visit 2: Study Day 1

The following procedures will be performed:

Pre-Dose

- Reassess inclusion/exclusion criteria
- Obtain blood samples for hematology, chemistry, coagulation, and lipid profile in a fasting state (does not have to be repeated if Screening visit is ≤ 7 days and there are no clinically significant findings)
- Perform a urine pregnancy test for all female subjects unless there is documented evidence confirming they are not of childbearing potential
- Perform the exercise bike test (CPET should occur in the morning after fasting for a minimum of 2 hours {if the subject has had a meal/snack}, with neither caffeine nor nicotine for at least 12 hours before testing)
- Perform a FARS-Neuro and clinician-rated CGI (severity of illness question only)
- Update medical history and demographics
- Complete the Speech Measurement Recording
- Record vital sign measurements and weight
- Obtain blood samples for biomarkers prior to the morning meal and dosing
- Randomize subject to study treatment group and dispense study drug
- Perform a physical examination
- Subject complete FARS ADL, SF-36, VAS (for Fatigue), Fatigue scale, Neuro-QoL scales, Speech Assessment questionnaire and Fall questionnaire
- Obtain T1MW and T25FW
- Obtain a 12-lead ECG (does not have to be repeated if Screening visit is ≤ 7 days and there are no clinically significant findings

Collect fall diary

Dosing

Subjects will take, as per the randomization scheme, the first dose of study drug at the clinic with a meal after all baseline testing is complete.

Post-Dose

- Record concomitant medications
- Record AEs

13.3. Days 30 (\pm 7 days), 60 (\pm 7 days), and 90 (\pm 7 days)

Subjects will be contacted by phone by a study site staff member and asked to complete the PGI-C, the Fatigue scale, the Neuro-QoL scales (lower extremity function and upper extremity function), and questions 8 and 9 of the Fall questionnaire. Subjects can scan and email questionnaires to the site. The site is to also confirm if the subject is taking study drug as instructed. Adverse events will also be assessed.

13.4. Visit 3: Day 120 (\pm 30 days)

The following procedures will be performed:

- Obtain blood samples for hematology, chemistry, coagulation, and lipid profile in a fasting state
- Perform a urine pregnancy test for all female subjects unless there is documented evidence confirming they are not of childbearing potential
- Record vital sign measurements and weight
- Obtain blood samples for PK and biomarkers prior to the morning meal and dosing
- Perform the exercise bike test (CPET should occur in the morning after fasting for a minimum of 2 hours, with neither caffeine nor nicotine for at least 12 hours before testing)
- Perform a FARS-Neuro and clinician-rated CGI
- Perform a physical examination
- Subject complete FARS ADL, SF-36, PGI-C, VAS, Fatigue scale, Neuro-QoL scales and Fall questionnaire
- Obtain T1MW and T25FW
- Obtain a 12-lead ECG

- Collect fall diary
- Perform drug accountability
- Record concomitant medications
- Record AEs

Dosing

• Subjects will take the morning dose of study drug at the clinic with their breakfast.

13.5. Day 150 (\pm 7 days), Day 180 (\pm 7 days) and Day 210 (\pm 7 days)

Subjects will be contacted by phone by a study site staff member and asked to complete the PGI-C, the Fatigue scale, the Neuro-QoL scales (lower extremity function and upper extremity function), and questions 8 and 9 of the Fall questionnaire. Subjects can scan and email questionnaires to the site. The site is to also confirm if the subject is taking study drug as instructed. Adverse events will also be assessed.

13.6. Visit 4: Day 240 (\pm 30 days)

The following procedures will be performed:

- Obtain blood samples for hematology, chemistry, coagulation, and lipid profile in a fasting state
- Perform a urine pregnancy test for all female subjects unless there is documented evidence confirming they are not of childbearing potential
- Record vital sign measurements and weight
- Obtain blood samples for PK and biomarkers prior to the morning meal and dosing
- Perform the exercise bike test (CPET should occur in the morning after fasting for a minimum of 2 hours, with neither caffeine nor nicotine for at least 12 hours before testing)
- Perform a FARS-Neuro and clinician-rated CGI
- Perform a physical examination
- Complete Speech Measurement recording.
- Subject complete FARS ADL, SF-36, PGI-C, VAS, Fatigue scale, Neuro-QoL scales, Speech Assessment questionnaire and Fall questionnaire
- Obtain T1MW and T25FW
- Obtain a 12-lead ECG

- Collect fall diary
- Perform drug accountability
- Record concomitant medications
- Record AEs

Dosing

• Subjects will take the morning dose of study drug at the clinic with their breakfast.

13.7. Day 270 (\pm 7 days) and Day 300 (\pm 7 days)

Subjects will be contacted by phone by a study site staff member and asked to complete the PGI-C, the Fatigue scale, the Neuro-QoL scales (lower extremity function and upper extremity function), and questions 8 and 9 of the Fall questionnaire. Subjects can scan and email questionnaires to the site. The site is to also confirm if the subject is taking study drug as instructed. Adverse events will also be assessed.

13.8. Visit 5: Day 330 (\pm 30 Days)

The following procedures will be performed.

- Obtain blood samples for hematology, chemistry, coagulation, and lipid profile in a fasting state
- Obtain a urinalysis sample (dipstick test, microscopic examination)
- Perform a urine pregnancy test for all female subjects unless there is documented evidence confirming they are not of childbearing potential. A Urine Pregnancy test kit will be provided to all female subjects (unless there is documented evidence confirming they are not of childbearing potential) to take home for the EOT visit. The site to instruct the subject that Pregnancy test has to be performed by the subject at home on the day of the EOT phone call (before the call and after the last dose)
- Record vital sign measurements, height, weight, and BMI
- Obtain blood samples for PK and biomarkers prior to the morning meal
- Perform the exercise bike test (CPET should occur in the morning after fasting for a minimum of 2 hours, with neither caffeine nor nicotine for at least 12 hours before testing)
- Perform a FARS-Neuro and clinician-rated CGI
- Perform a physical examination

- Subject complete FARS ADL, SF-36, PGI-C, VAS, Fatigue scale, Neuro-QoL scales, Speech Assessment questionnaire and Fall questionnaire
- Obtain T1MW and T25FW
- Obtain a 12-lead ECG
- Obtain an echocardiogram
- Collect fall diary
- Perform drug accountability, if applicable
- Record concomitant medications
- Record AEs

Dosing

• Subjects will take the morning dose of study drug at the clinic with their breakfast. Subjects to be reminded that the last dose of study drug has to be taken 4 weeks from the Day 330 visit.

13.9. Optional PK Profile Sub-Study

The following procedures will be performed on Day 1:

- A blood sample for PK will be obtained at hour -1.0 to -0.5 (pre-breakfast, pre-dose),
- Subjects will take the morning dose of study drug at the clinic with their breakfast,
- A blood sample for PK will be obtained hour $0.5 (\pm 5 \text{ min})$,
- A blood sample for PK will be obtained hour 1 (\pm 5 min),
- A blood sample for PK will be obtained hour 2 (\pm 10 min),
- A blood sample for PK will be obtained hour $4 (\pm 15 \text{ min})$ (pre-lunch),
- A blood sample for PK will be obtained hour 8 (\pm 15 min) (pre-dinner),
- A blood sample for PK will be obtained hour $12 (\pm 60 \text{ min})$ (post-dinner)

The following procedures will be performed on Day 2:

• A blood sample for PK will be obtained on Hour 24 (pre-dose, pre-breakfast)

Dosing:

- The subject will only take the morning dose on the PK collection day. They will skip the evening dose.
- The subject should resume regular dosing schedule after morning PK draw on Day 2.

13.10. End of Treatment call (4 weeks from Day 330 + 7 days)

Subjects will be contacted by phone by a study site staff member to make sure they have taken their last dose of study drug and to perform final drug accountability. The subject will be provided with instructions, so they can ship or return all unused study drug/ bottles to the site. If none, the subject can destroy the same.

Site to confirm a urine pregnancy test for all female subjects (unless there is documented evidence confirming they are not of childbearing potential) was performed on the day of the EOT call (before the call and after the last dose). The subject to share the result and email a scanned photo of the result for site records. Study site staff member to also collect AE information and confirm any change in concomitant medication since last visit. For any ongoing AEs at EOT, the site will follow up to conclusion or until stabilized.

13.11. Optional PK Washout Sub-Study

Depending on the timing of entry into the sub-study, the following procedures will be performed throughout the Optional Washout PK Sub-Study:

- A blood sample for PK will be obtained 7 days (\pm 1 day) after the last dose.
- A blood sample for PK will be obtained 4 weeks (\pm 7 day) after the last dose.
- A blood sample for PK will be obtained 12 weeks (\pm 7 day) after the last dose.
- A blood sample for PK will be obtained 24 weeks (\pm 7 day) after the last dose.

13.12. Unscheduled Visits

Procedures to be performed at any unscheduled visit are at the discretion of the Investigator, but should at least include safety, laboratory, and health examinations necessary for collection of AE information. Any procedure can be repeated at an unscheduled visit as needed.

13.13. Early Termination Visit

If the subject withdraws or is discontinued from the study the following safety procedures should be performed:

- Perform a complete physical examination
- Record vital sign measurements and weight
- Obtain a 12-lead ECG
- Obtain blood samples for hematology, chemistry, coagulation, and lipid profile
- Obtain a urinalysis sample (dipstick test, microscopic examination)
- Perform a urine pregnancy test for all female subjects unless there is documented evidence confirming they are not of childbearing potential

- Record AEs
- Record concomitant medications
- Perform drug accountability

14. STATISTICS

14.1. Statistical Plan

A complete description of analysis populations and statistical methods will be provided in a formal Statistical Analysis Plan that will be finalized prior to unblinding and statistical analysis.

Analysis populations

- All Patients Population: Any participant with any record in the database. This
 population includes both screening and randomized subjects. Population will be
 utilized for descriptive patient counts that include screening subjects.
- Intent-to-Treat (ITT) population: All participants randomized to treatment.
- Modified Intent-to-Treat (mITT) Population: All randomized subjects with at least one post-baseline efficacy evaluation will be included in the mITT population and will be analyzed as randomized. The mITT population will be analyzed for efficacy evaluations.
- Per Protocol (PP) Population: For programming purposes, they will be identified as having no major protocol violations as identified separately by the study team and the Sponsor prior to database lock. Analyses of the PP population will be analyzed as treated.
- Safety population: All participants who receive at least 1 dose of drug or placebo.

Demographic data will be presented using descriptive statistics (e.g., mean, standard deviation, median, and range). Exposure to study drug and reasons for discontinuation will be tabulated. Safety analyses will use the Safety population. Safety variables will be tabulated and presented for all subjects who receive study drug or placebo capsules. Adverse events will be coded using the Medical Dictionary for Regulatory Activities (MedDRA). The incidence of treatment-emergent AEs will be presented by system organ class and preferred term. Adverse events will be presented by severity and relationship to study drug. Changes from Baseline in clinical laboratory parameters and vital signs will be summarized across time. Shift tables will be provided for selected laboratory parameters. Physical examination results will be presented in listings.

Primary, secondary and exploratory efficacy analyses of the 11-month on-treatment period will use the mITT population and the per-protocol population unless otherwise specified.

Change from baseline (CFB) will be analyzed by comparing the change between treatment groups using a mixed model with repeated measures (MMRM). The MMRM will compare the estimated change from baseline between treatments for the primary endpoint. This analysis will assess whether there is a difference in estimated CFB between active and placebo groups at 11 months.

The primary analysis will use the ITT methodology and an MMRM methodology with a random slope and intercept for each individual. Due to the small sample size the model will be optimized by implementation of two risk scores (baseline and slope) that account for multiple baseline covariates in one variable. The risk scores will be derived from blinded data using the GST change from baseline values and generated using the baseline model covariates (excluding treatment and visit; baseline risk score) or the baseline model covariates*time interactions (slope risk score). The risk scores will be included as covariates in the model.

To calculate the baseline risk score, the GST change score is regressed on the covariates listed below. Individual coefficients for the baseline risk score are multiplied by individual covariate values and summed. A separate slope risk score is calculated for baseline covariates interacting with time.

The MMRM with primary outcome CFB value as the response variable will include the following covariates and fixed effects:

- baseline risk score:
 - baseline score for GST
 - age
- slope risk score:
 - baseline score for GST * time
 - age*time
- Time (continuous)
- Time by treatment interaction (time*treatment)
- baseline score for parameter of interest (if not in GST)
- site pooled by region (random effect)

Model assumptions will be evaluated. If the parametric assumptions are evaluated as inappropriate or violated, rank analogues will be advanced.

All secondary and exploratory endpoints CFB values will be analyzed using the MMRM described above. This analysis will assess whether or not there is a difference in estimated CFB values between treatment group and placebo at the 11-month model estimate using least squares means estimates from the MMRM model.

Speech measurement reporting will be analyzed by a third party vendor. A separate report will be provided.

Responder analyses will be run on MVO2 (primary), GST, T1MW, Peak Workload, mFARS, and CGI-C (functional assessment). Responder analyses are performed to illustrate the clinical meaningfulness of the relationship between treatment differences and efficacy outcomes on a per

person basis. Responder analyses will be assessed at change from baseline cutoffs at the overall quartiles for each of the three variables. Patients who die or are unable to perform the test during the study will be counted as non-responders. Patients who do not complete will be carried forward using the last observation carried forward and the imputed value at the study endpoint will be used for the responder analysis.

In addition to summarizing the results for each relationship between individual clinical responses and treatment multiple clinical responses will also be correlated with treatment using the five GST component outcomes individually. Those who experienced the following combined clinical responses will be summarized in terms of counts and percent:

• Improvement or stabilization on at least 1, 2, 3, 4, and all of the 5 responder endpoints.

The PK of D2-LA and H2-LA will be characterized in terms of minimum and maximum exposure at steady state, based on a validated assay. The PK of D2-LA and H2-LA in RBC, D2-ARA, and H2-ARA also will be characterized in terms of minimum and maximum exposure at steady state; the validation of the assays to characterize these concentration values has not yet been validated.

Full details of planned analyses will be provided in a separate statistical analysis plan.

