7.2. Key secondary endpoint

1. To demonstrate the efficacy of RT001 compared to placebo on an overall performance score based on a GST change from baseline to 11 months. The GST will be a combination of three endpoints (timed 1 minute walk test [T1MW], peak workload, and MVO2).

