8. INVESTIGATIONAL PLAN

8.1. Study Design

This is a randomized, double-blind, placebo-controlled study to evaluate the efficacy, safety, and tolerability in subjects with FRDA following the oral administration of study drug (active or placebo capsules).

Subjects will self-administer the study drug orally with meals. While on study drug, subjects are recommended to avoid eating foods high in PUFAs. Subjects will keep food journals from screening through the completion of month 1 on study drug. After month 1, subjects will keep 2-week food journals prior to next scheduled onsite visit. Subjects (or parents/caregivers, as applicable) will have an initial call and as needed with the diet coach to discuss food journal completion requirements.

A total 60 FRDA subjects will be enrolled. Subjects will be randomized to active [9 capsules of RT001 (8.64 g/day) for the first month, followed by 6 capsules of RT001 (5.76 g/day)] or placebo in a 1:1 ratio. Randomization will be stratified by FARS Neurological score: ≤45 and >45. Enrollment of patients with age > 25 will be capped at 25 % of the total enrollment.

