8.2. Randomization

The randomized, double-blind design of the study is intended to minimize bias on the part of subjects, investigators, and analysts. Subjects who meet all enrollment criteria and from whom consent has been obtained will be randomly assigned to receive one of two treatments (RT001 or placebo capsules) following a 1:1 ratio. Randomization will be stratified as much as possible according to the FARS Neurological score (baseline FARS score of \leq 45 and >45). Enrollment of patients with age > 25 will be capped at 25 % of the total enrollment.

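### The listed primary model leaves out the FARS randomisation stratum and MVO2's own baseline: a possible loss of precision, cheap to avoid before unblinding

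*Combined protocol and SAP*

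**What the plan says.** Sections 8.1 and 8.2 stratify the 1:1 allocation at a FARS score of 45: "Randomization will be stratified by FARS Neurological score" in the first and, more loosely, "Randomization will be stratified as much as possible according to the FARS Neurological score" in the second. The primary endpoint is change in MVO2 to 11 months (Section 7.1). Section 7.2 defines the composite: "The GST will be a combination of three endpoints (timed 1 minute walk test [T1MW], peak workload, and MVO2".

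Section 14.1 gives a mixed model for change from baseline with a random intercept and slope per subject. The listed terms are:
- a baseline risk score built from baseline GST and age
- a slope risk score built from the same two variables interacting with time
- continuous time, and time by treatment
- "baseline score for parameter of interest (if not in GST"
- pooled site as a random effect.

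The reason given for the scores is: "Due to the small sample size the model will be optimized by implementation of two risk scores". Their weights come from a blinded regression of GST change. The list has no FARS term and no reason is given for that. The same section leaves full methods to a separate SAP, to be final before unblinding, so this point concerns the list as it stands.

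**The concern.** A variable used to stratify randomisation is normally carried into the analysis. Balancing on it takes its variation out of the treatment comparison, and a model without it still counts that variation as noise.

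Own baseline is usually a useful covariate for a change score, because regression to the mean ties change to the starting value. The exception removes it for the primary endpoint and for both single-measure secondary endpoints. Baseline MVO2 survives only as one part of a composite, weighted by how well that composite predicts GST change rather than MVO2 change.

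At stake are the width of the primary interval and how far a chance baseline difference in MVO2 can shift the estimate. The documents give no effect size or SD for MVO2, so spare precision cannot be assumed.

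**Working it through.** **1. The plan's own figure.** Section 14.2 states over 99% power for peak workload with 30 per arm, difference 15.8, SD 11.1 and two-sided alpha 0.05. The standardised effect is 15.8/11.1 = 1.42. The noncentrality is 1.42 × √(30/2) = 5.5, and the noncentral t on 58 df gives 0.9997. The figure reproduces, but it is for peak workload and does not involve the terms at issue.

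**2. Stratum.** Let h be the share of Month-11 residual variance that the stratum explains beyond baseline GST and age. The documents do not give h; 2, 5, 10 and 20% are assumed, with two equal strata. The standard error without the stratum, relative to that with it, is about 1/√(1−h). If 11.1 is taken as the total within-group SD, the strata must differ by 2√h × 11.1 peak-workload units.

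| h | Stratum difference | 1/√(1−h) | SE ratio, simulated mixed model: full / half / no stratification | Type I error, single visit: full / none |
|---|---|---|---|---|
| 2% | 3.1 | 1.01 | 1.01 / 1.01 / 1.00 | 0.048 / 0.051 |
| 5% | 5.0 | 1.03 | 1.03 / 1.03 / 1.02 | 0.046 / 0.051 |
| 10% | 7.0 | 1.05 | 1.06 / 1.06 / 1.05 | 0.038 / 0.050 |
| 20% | 9.9 | 1.12 | 1.14 / 1.13 / 1.13 | 0.028 / 0.050 |

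The mixed-model column uses 60 subjects, visits at Months 4, 8 and 11, REML, and 2,000 trials per setting. Assumed variances are intercept 1, slope 1 per 11 months and residual 0.5. Risk scores are left out because h is defined as what remains after them. The 20% row is extreme: 9.9 exceeds in size both planning means (7.5 and −8.3). The wider standard error appears however well stratification was carried out; the conservatism does not.

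For the mixed model itself, type I error is less settled. Under full stratification the simulations above gave 0.044, 0.039 and 0.036 at 5, 10 and 20% (Monte Carlo SE 0.003), against a large-sample limit of 0.027 at 20%. Mixed-model simulations with other assumed variances, with and without a prognostic stratum, gave 0.046 to 0.057 (Monte Carlo SE about 0.006).

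Power at an assumed effect of 0.5 total SD (single visit, full stratification), without and with the stratum: 0.49/0.49, 0.48/0.50, 0.47/0.52 and 0.47/0.56.

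**3. Own baseline.** Assume three components with pairwise baseline correlation r, baseline-to-follow-up correlation ρ, and follow-up depending on the other components only through own baseline. With own baseline in the model, the residual variance of change is 1−ρ². With only the mean of the three, own baseline keeps unexplained variance 2(1−r)/3, which enters change with coefficient (1−ρ). The variance ratio is

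1 + [(1−ρ)/(1+ρ)] × 2(1−r)/3.

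- ρ = 0.9, r = 0.7: 1 + 0.0526 × 0.200 = 1.011; SE ratio 1.005.
- ρ = 0.6, r = 0.3: 1 + 0.25 × 0.467 = 1.117; SE ratio 1.057.

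Simulation at n = 60 over these ranges gave 0.996 to 1.047. Widening to ρ = 0.5, r = 0.3 gives a variance ratio of 1.16, or about 8% of the standard error.

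**4. Chance imbalance in baseline MVO2.** Among null trials with an imbalance above 2 SE, the listed terms in a Month-11 model rejected in 4.7 to 11.6%, depending on the scenario. In the scenario with 11.6%, adding own baseline brought it to 5.3%. In the mixed model, trials with an imbalance above 1.5 SE rejected in 4.7 to 9.4% with the listed terms and 6.2 to 7.8% with own baseline. These rest on 128 to 193 trials each, too few to rank the models. When the active arm's baseline was more than 1 SE higher, the mean mixed-model estimate was off by −0.018 to −0.116 (between-subject SD units) with the listed terms and by −0.009 to 0.019 with own baseline.

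**The case against.** The best defence is that no size for the stratum effect comes from the documents. Section 6.7 says progression is fastest soon after diagnosis, but that is about the disease in general, not MVO2. Section 6.4 reports that FARS-Neuro and the exercise measures correlate, so baseline GST and age may already carry what the stratum knows. This stands, and it makes the stratum part conditional.

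It can also be said that compressing covariates is a deliberate choice at 60 subjects and that the SAP is still to come. This stands in part. Small sample size explains the risk scores, but not the missing stratum. The plan also accepts one extra baseline term for every endpoint outside the GST, so economy of terms does not explain denying one to the primary endpoint. A pending SAP means the change can still be made.

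The planning power above 99% is no defence, because it is not for MVO2.

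The fuller model is not perfectly calibrated either. With the stratum terms added, simulated type I error averaged 0.054 over 12 settings of 2,000 trials. The Monte Carlo SE is √(0.05 × 0.95/24,000) = 0.0014, so this is about 2.8 SE above 0.05. It may reflect the t reference on 54 df rather than the stratum terms; the other mixed-model simulations, with own baseline also added, gave 0.050 to 0.055. The excess is small.

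A reader might infer that leaving out a stratification factor inflates false positives. Neither the documents nor the calculations support that: randomisation protects the overall error rate.

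**Conclusion.** Both omissions are plain in the text. The cost is possible precision, not validity:
- **Stratum:** the standard error is about 1, 3, 6 or 12 to 14% wider than needed at assumed shares of 2, 5, 10 or 20%, and no wider if the stratum adds nothing to baseline GST and age.
- **Own baseline:** roughly 0.5 to 6% of the standard error for assumed ρ of 0.6 to 0.9 and r of 0.3 to 0.7, because baseline GST recovers part of the information.

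Three stronger readings should be resisted. A reader might infer that precision is certainly lost through the stratum; the documents do not show that FARS predicts MVO2 change beyond the listed covariates. A reader might infer that the planned test is conservative; that holds for a single-visit test under full stratification (down to about 0.03 at the extreme share), but is not firmly shown for the specified mixed model, and Section 8.2 promises stratification only as far as possible. A reader might infer that false positives are no concern at all; the protection is unconditional, and the estimate is less protected once a chance imbalance in baseline MVO2 has occurred.

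This is a modest improvement worth making. It does not threaten the trial's conclusions.

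**What to change.** Before unblinding, in the SAP:
1. Add the FARS stratum and stratum-by-time to the models for MVO2, GST, T1MW and peak workload.
2. Include own baseline by name for MVO2, T1MW and peak workload. Keep the exception only for the GST endpoint, whose baseline is already in the risk scores.

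If the sponsor prefers the listed model, the SAP should say why baseline GST and age are enough.

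The cost is SAP wording, about three degrees of freedom (stratum, stratum-by-time, own baseline) and no new data. If the terms explain nothing, the standard error grows by about 1%.

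Two neighbouring inconsistencies in Section 14.1 need reconciling as separate points. Section 7.2 names three GST components, while the responder text speaks of "using the five GST component outcomes individually", which leaves the reach of the exception unclear. The risk scores are built from "baseline model covariates (excluding treatment and visit; baseline risk score", which implies treatment and visit terms, but the list has only continuous time and "Time by treatment interaction (time*treatment".
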